#### 11.1.2. Analysis Plan

Normal quantile plots of  $SUV_{max}$  for each scanner will be prepared to assess to what extent the distribution can be approximated by the normal distribution, and to suggest a suitable transformation if not. The distribution of  $SUV_{max}$  for each scanner will be summarized with means, standard deviations, range, median and upper and lower quartiles. The distribution of the difference ( $SUV_{max}$ \_PET/CT –  $SUV_{max}$ \_PET/MRI) (difference of transformed values if applicable) will likewise be summarized. Cumulative distribution (waterfall plots) may be prepared to assist in the evaluation of the results. Patient clinical and demographic characteristics will be summarized using relevant summaries (proportions for categorical variables, means and standard deviations for continuous variables.

The mean difference plus or minus twice the standard deviation of the difference will be calculated as a measure of absolute accuracy. The relative accuracy will be calculated by dividing the preceding interval by the arithmetic average of the mean  $SUV_{max}$  of the two scanners. The interpretation of these intervals is that we can expect that approximately 95% of future differences to lie in these intervals. A paired t-test will be used to aid in the interpretation of the results. Sensitivity analyses may be conducted using linear mixed effects models to account for possible clustering of lesions within patients.

The difference of  $SUV_{max}$  measures will be correlated with patient and lesion characteristics and with time after injection using the appropriate method (Pearson correlation for continuous variables such as age and time from injection, two-sample t-tests for binary attributes (sex) and analysis of variance for categorical variables).

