#### 11.6. Sample Size

Data from Kershah (*10*) shows coefficients of variation between SUV measurements between PET/CT and PET/MRI ranging from 0.21 to 0.51, about 0.33 for CT attenuation correction and 0.38 for MR attenuation correction. We present calculations assuming a CV of 0.38 for both modalities and a Pearson correlation of 0.5 (moderate scenario) and 0.9 (optimistic scenario). Assuming a Pearson correlation of 0.5 on the log scale, 200 subjects provide 80% power to detect a relative difference of 8% between the SUVmax values using the two modalities. With an optimistic assumption of a Pearson correlation of 0.9, 200 patients provide 80% power to detect a relative difference of 3.4%. These differences do not seem minute, they will be a bit larger with only 100 subjects: assuming a Pearson correlation of 0.5 on the log scale, 100 subjects provides 80% power to detect a relative difference of 11% between the SUVmax values using the two modalities. With an optimistic assumption of a Pearson correlation of 0.5 on the log scale, 100 subjects provides 80% power to detect a relative difference of 11% between the SUVmax values using the two modalities. With an optimistic assumption of a Pearson correlation of 0.9, 200 patients provide 80% power to detect a relative difference of 5%.

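### Section 11.6 gives two detectable differences, 3.4% and 5%, for the same 200 patients at correlation 0.9; the 5% belongs to 100 patients

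*Combined protocol and SAP*

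**What the plan says.** Section 11.6 (Sample Size) sets one CV and two correlations: "We present calculations assuming a CV of 0.38 for both modalities and a Pearson correlation of 0.5 (moderate scenario) and 0.9 (optimistic scenario"). It then gives these results, each at 80% power:

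- Correlation 0.5: "200 subjects provide 80% power to detect a relative difference of 8"%.
- Correlation 0.9: "200 patients provide 80% power to detect a relative difference of 3.4"%.
- After a remark that "they will be a bit larger with only 100 subjects", correlation 0.5 again: "100 subjects provides 80% power to detect a relative difference of 11"%.
- The 11% result a second time, now labelled differently: "With an optimistic assumption of a Pearson correlation of 0.5 on the log scale, 100 subjects provides 80% power".
- Last sentence: "With an optimistic assumption of a Pearson correlation of 0.9, 200 patients provide 80% power to detect a relative difference of 5"%.

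Sections 11.7 and 11.8 put the planned accrual at 100 patients. The Analysis Plan (11.1.2) names the test: "A paired t-test will be used to aid in the interpretation of the results". Neither alpha nor sidedness is stated.

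**The concern.** The second and last results in that list have the same number of patients, correlation and power, and nothing in the section says that another input changed between them. One set of inputs has one detectable difference, so at least one of the two is wrong.

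Section 11.6 is the only justification of the sample size. Read literally, it offers two incompatible results for 200 patients at correlation 0.9 and none at correlation 0.9 for the 100 patients the trial plans to enrol. A reader could conclude that 200 patients are needed to detect 5% in the optimistic scenario, or could be unable to tell what the planned study can detect in that scenario.

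**Working it through.** **Inputs.** From section 11.6: CV 0.38 for both scanners; correlation ρ = 0.5 or 0.9, on the log scale; N = 200 or 100; power 80%. From section 11.1.2: paired t-test. Assumed, because the documents do not say: two-sided alpha 0.05, and one independent SUVmax pair per patient.

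**Step 1. Which figure is out of line, using only the section's own results.** At fixed power and alpha, in large samples, the detectable log difference is proportional to √((1 − ρ)/N). This check needs neither alpha nor the CV.

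- 200 to 100 patients at ρ = 0.9 (multiply by √2): ln(1.034) = 0.03343; × 1.4142 = 0.04728; exp − 1 = **4.8%**.
- ρ from 0.5 to 0.9 at 100 patients (divide by √(0.5/0.1) = √5): ln(1.11) = 0.10436; ÷ 2.2361 = 0.04667; exp − 1 = **4.8%**.
- ρ from 0.5 to 0.9 at 200 patients: ln(1.08) = 0.07696; ÷ 2.2361 = 0.03442; exp − 1 = **3.5%**. If the stated 8% is rounded from 7.5% to 8.5%, the range is 3.3% to 3.7%. That covers 3.4% and excludes 5%.
- Reverse check: if 5% held at 200 patients and ρ = 0.9, then at ρ = 0.5 the figure would be ln(1.05) = 0.04879; × 2.2361 = 0.10910; exp − 1 = **11.5%**. The section states 8%.

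So 8% and 11% both fit 3.4% at 200 patients, and 5% fits 100.

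**Step 2. Direct calculation.** With s the SD of log SUVmax, the SD of the paired difference is s√(2(1 − ρ)). The normal approximation to the detectable log difference is d = (1.960 + 0.842) × SD/√N, and the relative difference is exp(d) − 1. Taking s = 0.38:

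- ρ = 0.9: SD = 0.38 × √0.2 = 0.1699. N = 200: d = 2.802 × 0.1699/14.142 = 0.0337, or 3.4%. N = 100: d = 2.802 × 0.1699/10 = 0.0476, or 4.9%.
- ρ = 0.5: SD = 0.38 × √1 = 0.38. N = 200: d = 0.0753, or 7.8%. N = 100: d = 0.1065, or 11.2%.

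The exact paired t calculation (noncentral t) is shown below for two readings of the CV: as the log SD itself (0.38), and converted by √ln(1 + 0.38²) = 0.367.

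| N | ρ | Stated in 11.6 | Log SD 0.38 | Log SD 0.367 |
|---|---|---|---|---|
| 200 | 0.5 | 8% | 7.86% | 7.58% |
| 200 | 0.9 | 3.4%, then 5% | 3.44% | 3.32% |
| 100 | 0.5 | 11% | 11.35% | 10.95% |
| 100 | 0.9 | none | 4.93% | 4.76% |

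With log SD 0.38, the stated 8%, 3.4% and 11% all reproduce to the precision printed. The 5% reproduces only in the row for 100 patients.

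**Step 3. Power for a 5% difference at ρ = 0.9.** With 200 patients: 98.1% (log SD 0.38) or 98.7% (0.367). With 100 patients: 81.1% or 83.7%. With log SD 0.38, 98 patients are enough for 80%.

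**Step 4. Can another input rescue 5% at 200 patients?** At ρ = 0.9 and log SD 0.38, two-sided alpha 0.10 gives 3.04% and 0.01 gives 4.23%; neither gives 5%. At alpha 0.05 the log SD would have to be 0.04879 × √200/(2.802 × √0.2) = 0.55, against the 0.38 the section fixes and above the top of the CV range it quotes (0.21 to 0.51).

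**The case against.** The contradiction is hard to dispute; the fair counter-argument is about weight.

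- The faulty sentence names 200 patients, a size the trial does not plan to reach.
- The less favourable result for the planned size, 11% at correlation 0.5, is printed correctly.
- The value 5% is itself right for 100 patients, and the lead-in about having only 100 subjects lets a careful reader recover it.
- No target difference is named, so no decision turns on 5%.
- The paired t-test is only an aid to interpretation; the analysis rests mainly on the mean difference plus or minus two standard deviations.
- The duplicated sentence and the missing alpha are editorial matters and should not add weight.
- The exact percentages depend on how the CV is turned into a log SD, on an assumed alpha, and on one pair per patient, whereas the primary analysis is per lesion.

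Most of this stands, and it limits the consequence: neither the planned size nor the analysis is affected. It does not remove the error. A stated power figure is false as written, and it is the only result at correlation 0.9 that could apply to the planned 100 patients. The dependence on assumptions is met by giving ranges; the contradiction itself, and the scaling check in step 1, need neither alpha nor the CV. The per-lesion analysis is a separate question and does not reconcile two results from identical inputs.

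**Conclusion.** The concern holds. Section 11.6 gives 3.4% and 5% for identical inputs, and the second is wrong as written. At 200 patients and correlation 0.9 the detectable difference is 3.3% to 3.4%; at 100 patients it is 4.8% to 4.9%, which rounds to 5%. Power for 5% with 200 patients is 98% to 99% rather than 80%. These ranges cover both readings of the CV and rest on two-sided alpha 0.05 and one pair per patient. That the last number should read 100 is an inference, though a strong one: the arithmetic, the sentence's position after the remark on 100 subjects, and the planned accrual all point to it. The sentence just before it, which repeats the 11% result and calls 0.5 optimistic where the section defines it as moderate, suggests a copying fault in the same lines. The consequence is confined to the reported justification.

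**What to change.** Check the last sentence of section 11.6 against the sponsor's own calculation and, once confirmed, change its patient number from 200 to 100, keeping 5%. Delete the second 11% sentence, which mislabels correlation 0.5 as optimistic. Add the alpha and sidedness used, so that the figures can be reproduced. The cost is a text correction and one look at the sponsor's calculation; the number of patients, the data collected and the analysis stay as they are.

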#### 11.7. Accrual estimates

We expect the accrual of 100 patients. There are approximately 4500 patients scanned each year using PET/CT for cancer, of which approximately 100 patients are Ga68 DOTA TATE PET/CT patients. We plan to enroll 15 participants/year and this is easily achievable given our experience with other protocols.

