#### 3.4 Study Timeline

#### 3.4.1 Primary Completion:

The study will reach primary completion 24 months from the time the study opens to accrual.

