#### 3.4.2. Study Completion:

The study will reach study completion 48 months from the time the study opens to accrual.

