#### 7. STUDY CALENDAR

	Pre- Study	Week 1	12 Months
Informed consent	х		
Demographics	Х		
Medical history	Х		
 F FDG or  Ga DOTA TATE PET/CT and PET/MRI done on the same day		x	
Data analysis			Х

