#### **10.3 Measurement Time Points**

SUVmax values of the lesions will be measured after the scan completion.

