#### 11.8. Criteria for future studies

At this time there are no future studies planned beyond the initial 100 participants.

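### The target of 100 patients, the rate of 15 a year and completion at 24 and 48 months cannot all hold; Section 11.6 also gives two detectable differences for one case

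*Combined protocol and SAP*

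**What the plan says.** On the total, Section 11.7 states "We expect the accrual of 100 patients", and Section 11.8 repeats it: "At this time there are no future studies planned beyond the initial 100 participants".

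On the rate, the only figure is in Section 11.7: "We plan to enroll 15 participants/year and this is easily achievable given our experience with other protocols". The sentence just before it describes the pool: "There are approximately 4500 patients scanned each year using PET/CT for cancer, of which approximately 100 patients are Ga68 DOTA TATE PET/CT patients".

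On the dates, Section 3.4.1 reads "The study will reach primary completion 24 months from the time the study opens to accrual" and Section 3.4.2 reads "The study will reach study completion 48 months from the time the study opens to accrual".

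On the time each patient contributes, the Study Calendar (Section 7) has "DOTA TATE PET/CT and PET/MRI done on the same day", in week 1. Section 10.3 says of the SUVmax that "values of the lesions will be measured after the scan completion".

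Section 11.6 assumes a CV of 0.38 for both modalities and a correlation of 0.5 (called moderate) or 0.9 (called optimistic). At 80% power it gives these detectable relative differences, in this order:

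- 200 subjects, correlation 0.5: 8%
- 200 patients, correlation 0.9: 3.4%
- after a remark that the differences grow somewhat with only 100 subjects: 100 subjects, correlation 0.5: 11%
- the same 100-subject, correlation 0.5, 11% result again, now labelled optimistic
- 200 patients, correlation 0.9: 5%

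**The concern.** The total, the rate and the dates are tied together by simple multiplication, and the stated values do not fit. The document does not say which one gives way. If the total governs, the study overruns its dates by years. If the dates and the rate govern, the study ends with a fraction of the patients on which its precision was judged.

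In Section 11.6, one design (200 patients, correlation 0.9, 80% power) cannot have two detectable differences. The only optimistic-scenario figure meant for the planned 100 patients is printed against 200. A reader therefore cannot take the intended precision of the actual study straight from the text.

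**Working it through.** **Accrual.** Inputs: total 100 (Sections 11.7 and 11.8), rate 15 a year (11.7), 24 and 48 months from opening (3.4.1 and 3.4.2). Patients = rate × time.

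- By 24 months: 15 × 2 = 30.
- By 48 months: 15 × 4 = 60.
- Time to 100: 100 / 15 = 6.67 years = 80 months.
- Rate needed for 100 by 24 months: 100 / 2 = 50 a year, or 50 / 15 = 3.3 times the stated rate.
- Rate needed for 100 by 48 months: 100 / 4 = 25 a year, or 25 / 15 = 1.7 times the stated rate.

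Follow-up cannot fill the gap. Both scans are done on one day and the primary measurement is read from them, so primary completion at 24 months with 100 patients needs all 100 scanned by then. The calendar also places data analysis in a 12-month column. If that interval has to fit inside the 24 months, the accrual window is shorter still.

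If 15 a year is only the 68Ga DOTA TATE rate, the unstated FDG rate would have to be (100 − 30) / 2 = 35 a year for 24 months, or (100 − 60) / 4 = 10 a year for 48 months.

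**Section 11.6 without assuming alpha.** For a fixed test and power, the detectable log difference is proportional to 1/√n. Moving from 200 to 100 patients multiplies it by √2:

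- Correlation 0.9: exp(ln 1.034 × √2) − 1 = exp(0.0334 × 1.414) − 1 = 4.84%, which rounds to 5%.
- Correlation 0.5, in reverse: exp(ln 1.11 / √2) − 1 = 7.66%, which rounds to the stated 8%.

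So 8% and 11% form a 200/100 pair, and so do 3.4% and 5%.

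**Section 11.6 from the stated inputs.** The plan gives neither alpha nor sidedness; two-sided 0.05 is assumed. This is a paired t-test on the log scale with one pair per patient, using the noncentral t. The SD of the difference is s√(2(1 − ρ)), with s = √ln(1 + 0.38²) = 0.367 or s = 0.38 taken directly. The relative difference is exp(d) − 1. The table shows both choices of s; n = 60 and n = 30 are added for the accrual question.

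| n | ρ = 0.5 | plan | ρ = 0.9 | plan |
|---|---|---|---|---|
| 200 | 7.58 / 7.86% | 8% | 3.32 / 3.44% | 3.4% and 5% |
| 100 | 10.95 / 11.35% | 11% | 4.76 / 4.93% | none |
| 60 | 14.46 / 15.00% | – | 6.23 / 6.45% | – |
| 30 | 21.45 / 22.28% | – | 9.08 / 9.41% | – |

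The stated 8%, 3.4% and 11% reproduce to rounding. The 5% reproduces only at n = 100. At n = 200 and ρ = 0.9, power for a 5% difference is 98.7 / 98.1%, not 80%; at n = 100 it is 83.7 / 81.1%. One-sided 0.05 fits less well: by the normal approximation with s = 0.38 it gives 6.9%, 3.0%, 9.9% and 4.3% for the four cases.

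**Effect on the planned interval, only if enrolment stopped at 60 or 30.** The plan reports the mean difference plus or minus twice the SD. With one pair per patient, the standard error of each limit is about SD × √(1/n + 4/(2(n − 1))), which is 0.174, 0.225 and 0.320 SD for n = 100, 60 and 30. Multiplying by t(0.975, n − 1) gives 95% half-widths of 0.34, 0.45 and 0.65 SD. The expected width of the interval itself does not change.

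**The case against.** **The rate may be for a subgroup.** It follows a sentence ending on 68Ga DOTA TATE patients, and 15 of about 100 such patients a year is plausible. On that reading the three figures need not conflict. But Section 11.7 says participants without naming a tracer, and Section 11.8 uses the same word for all 100. Even if the reading is right, the section on accrual then gives no overall rate, so it supports neither completion date.

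**The pool is large.** With about 4500 cancer PET/CT scans a year, 100 patients look easy to find. This shows that a faster rate may be possible. The plan still states 15.

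**The consequences are conditional.** Nothing says enrolment stops at 24 or 48 months, and if the target governs, the power at 100 is untouched. The figures for 30 and 60 patients also take one pair per patient, whereas the primary analysis counts lesions, and the plan does not propose confidence intervals around the limits of its interval. All of this stands; those figures show what is at stake and are not a forecast.

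**The slip in Section 11.6 is harmless.** Its context points to 100, it errs towards understating power, and the paired t-test only aids interpretation (Analysis Plan under Section 11.5). This also stands as to consequence. The printed statement is nevertheless wrong, and it concerns the planned sample size.

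**Conclusion.** Both points hold. With 15 a year read as the overall rate, which is the plain reading, enrolment reaches 30 by 24 months and 60 by 48, against a target of 100 that takes 80 months. This needs no statistical assumption. With 15 a year read as a subgroup rate, the defect is a missing overall rate.

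In Section 11.6, the last patient number should be 100. The √2 scaling shows this without an alpha, and the full calculation agrees under an assumed two-sided 0.05. The sentence before it is a duplicate with the wrong scenario label.

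The reach is limited: no decision rule or planned procedure changes, and the power at 100 patients is as intended if 100 are enrolled. Only if enrolment stopped at the stated dates and rate would the detectable difference rise from about 11% to about 15% (60 patients) or 21–22% (30 patients) at correlation 0.5, and from about 5% to about 6% or 9% at correlation 0.9. It should be corrected, and confidence in the finding is high.

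**What to change.** Make Sections 3.4, 11.7 and 11.8 agree in one of three ways:

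1. Correct the rate: 50 a year for completion in 24 months, or 25 a year for 48 months with primary completion moved accordingly. If 15 a year is the 68Ga DOTA TATE rate, say so and add the overall rate.
2. Keep 15 a year and 100 patients, and move the completion dates to about 80 months.
3. Keep the rate and the dates, and restate the total as 30 or 60 with the detectable differences for that number.

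The documents give neither PET/MRI capacity nor a consent rate, so the choice is the sponsor's. Whichever is chosen, state whether the 12-month data-analysis entry in Section 7 is per patient or for the whole study, and whether it falls within the time to primary completion.

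In Section 11.6, change the patient number in the final sentence from 200 to 100, delete the duplicated correlation-0.5 sentence labelled optimistic, and state the alpha and sidedness used.

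The edits cost only text and add no procedures. Options 1 and 2 commit the site to faster enrolment or a longer study, and the documents do not allow that cost to be estimated. Only option 3 makes the stated precision less favourable.

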#### 11.8. Criteria for future studies

At this time there are no future studies planned beyond the initial 100 participants.

Appendix: Inclusion/Exclusion Criteria Checklist

A	Inclusion Criteria (From IRB approved protocol)	Yes	No	Supporting Documentation*
  1.	Patient is ≥ 18 years old at the time of the drug administration			
s 2.	Patient provides written informed consent			
ა კვ.	Patient is diagnosed with cancer			
b 4. j	Patient is capable of complying with study procedures			
e c5. t	Patient is able to remain still for duration of imaging procedure (about one hour)			
	Exclusion Criteria (From IRB approved protocol)			
1.	Patient is < 18 years old at the time of the drug administration			
2.	Patient is pregnant or nursing			
3.	Metallic implants (contraindicated for MRI)			
4.	Renal function impairment preventing administration of MRI contrast (only for patients receiving contrast)			

